1.4 STUDY PROCEDURE

This study includes screening stage V1, cell collection stage V2, baseline stage V3 (0-5 days before cell transplantation), REGEND001 autologous therapy product transplantation stage V4, follow-up stage V5-V9, safety follow-up stage after research. Follow-up stage includes: V5 (24 hours \pm 4 hours after transplantation), V6 (1 week \pm 2 days after transplantation), V7 (4 weeks \pm 3 days after transplantation), V8 (12 weeks \pm 5 days after transplantation), V9 (24 weeks \pm 7 days after transplantation). During the study, the vital signs, laboratory examinations, 12-lead electrocardiogram, chest HRCT, pulmonary functions, 6-minute walking distance, questionnaires, concomitant medications, adverse events, etc. will be checked and recorded.

Screening stage V1: After the patient signing the informed consent, relevant physical examination and check of previous physical examination will be done. The investigator will check inclusion and exclusion criteria, making judgement on whether the patient is eligible.

Cell collection stage V2: Tissue collection through bronchoscopy, cell isolation and expansion of around 4-8 weeks before autologous transplantation of REGEND001 autologous therapy product.

Baseline stage V3 (0-5 days before cell transplantation): 4-8 weeks later, conduct relevant examinations again and check inclusion and exclusion criteria. For idiopathic pulmonary fibrosis patients who are still eligible, they can formally join in this clinical trial and will receive autologous transplantation of REGEND001 cell products.

Cell transplantation stage V4 (the day of cell transplantation): According to the dose group each patient was assigned, a single administration of REGEND001 cell products at the corresponding dose were autologously transplanted to different lung segments through bronchoscopy. Investigator should be on site during the transplantation, confirming the dose, starting and stopping time of the transplantation, and recording correctly. Close observation of the patients in the outpatient or hospital for 2-4 hours after administration, and the investigator will determine when the patients can leave based on the tolerance of the patients. After leaving the hospital, the patients should return back to the research center as required for follow-up.

Follow-up stage: The patients will stop receiving REGEND001 during the follow-up stage, and continue with usual treatment which can be adjusted according to the doctor's orders.

Each patient will be followed up for 24 weeks after the administration, with a total of 5 visits. The follow-up time points

including V5 (24 hours \pm 4 hours after transplantation), V6 (1 week \pm 2 days after transplantation), V7 (4 weeks \pm 3 days after transplantation), V8 (12 weeks \pm 5 days after transplantation), and V9 (24 weeks \pm 7 days after transplantation). During the study, check and record the vital signs, laboratory examinations, 12-lead electrocardiogram, chest HRCT, pulmonary functions, 6-minute walking distance, questionnaires, concomitant medications, adverse events, etc.

If the patients undergo adverse events/severe adverse events, the situation should be documented in detail and followed up until the outcome is clear.

Safety follow-up stage after research: After the end of the follow-up stage in this study, the patient will enter the post-study safety follow-up until the patient's death or lost. The patient will be followed up once each at 1, 2, 3, 5, 8, and 10 years after treatment, and then once every five years.

Study Flowchart-----Each Dose Group

	Screening Stage	Cell Collection Stage	Baseline Stage ¹⁷	Cell Transplantation Stage	Follow-up Stage					
Content	14 days	1 day	0-5 days before transplantation	1 day	24 hours ± 4 hours after transplantation	1 week ± 2 days after transplantation	4 week ± 3 days after transplantation	12 week ± 5 days after transplantation	24 week ± 7 days after transplantation	Withdraw in advance ¹⁸
Stage Code	V1	V2	V3	V4	V5	V6	V7	V8	V9	
Sign Informed Consent	X									
Check Inclusion/Exclusion Criteria	X		X							
Demographic Characteristics ¹	X									
Medical History and Diagnosis ²	X									
Symptoms and Physical Examination ³	X	X	X	X	X	X	X	X	X	X
Vital Signs ⁴	X	X	X	X	X	X	X	X	X	X
Blood Routine, Urine Routine ⁵	X		X			X	X	X	X	X
Blood Chorionic Gonadotropin Blood Test ⁶	X		X						X	X
Blood Biochemistry Test ⁷	X		X			X	X	X	X	X
Arterial Blood Gas Test ⁸			X					X	X	X

Adverse Events		X	X	X	X	X	X	X	X	X
Severe Adverse Events		X	X	X	X	X	X	X	X	X

Note:

1. Including date of birth, gender, and ethnic.
2. Medical history: history of the present illness, past medical history, history of food and drug allergies, smoking history, drinking history, drug history, history of substance abuse.
3. Physical examination: skin mucous membrane, lymph nodes, head and neck, chest, abdomen, spine and limbs, musculoskeletal system, nervous system.
4. Vital signs: blood pressure, pulse, breathe, body temperature.
5. Blood routine: white blood cell count (WBC), neutrophil count (Neu), lymphocyte count (Lym), monocyte count (Mon), eosinophil count (Eos), basophil count (Bas), red blood cell count (RBC), hemoglobin (HGB), hematocrit (HCT), mean corpuscular volume (MCV), mean corpuscular hemoglobin concentration (MCHC), platelet (PLT). Urine routine: urine glucose (U-GLU), ketone bodies (KET), urine bilirubin (BIL), urobilinogen (UBG), urine protein (PRO), urine latent blood (BLD), urine pH, urine specific gravity (SG), urine red blood cells (URBC), urine white blood cells (UWBC).
6. Human chorionic gonadotropin (HCG): only for female patients (unapplicable for those who have been menopausal for more than a year).
7. Blood biochemistry: total protein (total protein), albumin (ALB), total bilirubin (TBIL), direct bilirubin (DBIL), alanine aminotransferase (ALT), aspartate aminotransferase (AST), alkaline phosphatase (ALP), γ -glutamyl transpeptidase (GGT), lactate dehydrogenase (LDH), urea (UREA), creatinine (Cr), uric acid (URIC), creatine kinase (CK), blood glucose (Glu), potassium (K^+), sodium (Na^+), chloride (Cl^-), calcium (Ca^{+}).
8. Arterial blood gas test: pH, PaCO₂, PaO₂, HCO₃.
9. Blood coagulation test: international normalized ratio (INR), activated partial thromboplastin time (APTT).
10. Myocardial enzyme spectrum: creatine kinase (CK), creatine kinase isoenzymes MB (CK-MB), lactate dehydrogenase (LDH).
11. Autoantibody test: antinuclear antibodies (ANA), extractable nuclear antigen (ENA) antibodies, cyclic citrullinated peptide (CCP) antibodies, antineutrophil cytoplasmic antibodies (ANCA).
12. Lung cancer markers: cytokeratin 19 fragment (CYFRA21-1), neuron-specific enolase (NSE), squamous cell carcinoma (SCC) antigen, carcinoembryonic antigen (CEA), carbohydrate antigen 125 (CA125).
13. Serological examination for syphilis, HIV, HBV, HCV: Qualitative test for HBV first. If its outcome is positive, do a quantitative measure for HBV next.
14. 12-lead electrocardiogram: heart rate, PR interval, QRS complex, QT interval (uncorrected), corrected QT interval QTc (QT/RR^{1/2}), and an overall comment (normal, abnormality without clinical significance, abnormality with clinical significance, need more interpretation). The original electrocardiogram with signature will be stored in research center, the results of electrocardiogram examination are recorded on CRF or eCRF.

15. Lung function (ventilation, diffusion): height, weight, forced vital capacity (FVC), forced expiratory volume in 1 second (FEV1), ratio of FEV1 to FVC, diffusing capacity of the lungs for carbon monoxide (DLCO), alveolar ventilation (VA), the ratio of diffusing capacity of the lungs for carbon monoxide to alveolar ventilation (DLCO/VA). DLCO is measured with single-breath method. The examination results within 3 months before cell therapy can be accepted as the lung function test result at the baseline stage.

16. Idiopathic pulmonary fibrosis acute exacerbation: an acute, clinically significant respiratory deterioration without clear cause, acute worsening of dyspnea and decreased lung function, leading to respiratory failure or even death.

17. Patients should be checked again for inclusion at baseline stage. Results of myocardial enzyme spectrum, autoantibody test, lung cancer markers, serological examination for syphilis, HIV, HBV, HCV, and chest HRCT at the screening stage can be accepted.

18. If abnormality with clinical significance was reported when the patient withdraws in advance, the patient should be followed up until the recovery from the adverse events, reaching a stable status or other clear outcomes as required by the investigator

1.5 FOLLOW-UP PLAN

All follow-up visits during the trial: V5 (24 hours \pm 4 hours after transplantation), V6 (1 week \pm 2 days after transplantation), V7 (4 weeks \pm 3 days after transplantation), V8 (12 weeks \pm 5 days after transplantation), V9 (24 weeks \pm 7 days after transplantation). During the study, the vital signs, laboratory examinations, 12-lead electrocardiogram, chest HRCT, pulmonary functions, 6-minute walking distance, questionnaires, concomitant medications, adverse events, etc. will be checked and recorded.

(1) After collecting lung tissue specimens through bronchofiberscope, keep the patient under close observation for 2 hours. The investigator will determine whether the observation period should be extended according to the tolerance of the patient;

(2) After cell transplantation through bronchofiberscope, keep the patient under close observation in the outpatient or hospital for 2-4 hours after administration, and the investigator will determine when the patients can leave based on the tolerance of the patients.

Safety follow-up stage after research: After the end of the follow-up stage in this study, the patient will enter the post-study safety follow-up until the patient's death or lost. The patient will be followed up once each at 1, 2, 3, 5, 8, and 10

years after treatment, and then once every five years. The follow-up measures include lung function, chest HRCT, and survival. This is not included in the 24-week follow-up, for the patient's knowledge only.

1.6 CRITERIA FOR DOSE ESCALATION TERMINATION

(1) Adverse events that occurred throughout the study period were assessed and graded according to CTCAE V5.0. Dose escalation should be terminated with one or more adverse events that were the same or similar and believed to be related (possibly, probably or definitely related) to the REGEND001 autologous therapy product reported on two or more patients of the same dose group after autologous transplantation:

1) hematological toxicity related to cell therapy

a) grade 4 neutropenia (ANC) for 3 days or more; or grade 3 and higher neutropenia with fever ($ANC < 1000/mm^3$ with a single measure of oral temperature $> 38.3^\circ C$ or $\geq 38.0^\circ C$ for one hour);

b) grade 3 thrombocytopenia ($25 \times 10^9/L \leq$ platelet counting $< 50 \times 10^9/L$) with overt clinical bleeding symptoms, or grade 4 thrombocytopenia (with or without overt clinical bleeding symptoms);

c) other grade 4 hematological toxicity.

2) non-hematological toxicity related to cell therapy

grade 3 and higher non-hematological toxicity, except:

a) under medical intervention, grade 3 non-hematological toxicity lasting ≤ 72 hours (non-laboratory examination, such as nausea, vomiting, or diarrhea, etc.);

b) under medical intervention, grade 3 or 4 non-hematological toxicity of abnormal in laboratory examination lasting ≤ 7 days (laboratory examination, such as arrhythmia, cardiac insufficiency, and nervous system abnormalities);

c) other toxicity that is higher than baseline level and related to cell therapy, classified as clinically meaningful severe and/or unacceptable toxicity by investigator and sponsor.

(2) Acute IPF exacerbation and severe adverse events that are related (possibly, probably or definitely related) to REGEND001 cell therapy;

(3) Adverse events that making investigator and sponsor believe the dose should not be escalated anymore, regardless of the event grade or reason;

(4) If none toxicity that would terminate dose escalation happened under the highest 3.3 times standard dose, investigator and sponsor will discuss together regarding

whether dose escalation should continue; if discontinued, the study will stop.

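### Section 1.6 exempts unacceptable toxicity and files cardiac and nervous system events as laboratory findings, so criterion (1) misses some treated grade 3 events

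*Protocol*

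**What the plan says.** Protocol section 1.6, criterion (1), ends escalation when the same or similar related events occur in two or more patients of one dose group. Its two parts are built differently.

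- **Haematological toxicity, 1).** All three items are counted events. The last is a catch-all, "other grade 4 hematological toxicity".
- **Non-haematological toxicity, 2).** The rule counts "grade 3 and higher non-hematological toxicity, except" and then lists a), b) and c) in one series:
  - a) "under medical intervention, grade 3 non-hematological toxicity lasting" up to 72 hours. This is for non-laboratory events, with nausea, vomiting and diarrhoea as examples.
  - b) "under medical intervention, grade 3 or 4 non-hematological toxicity of abnormal in laboratory examination lasting" up to 7 days. The examples given for this item are "laboratory examination, such as arrhythmia, cardiac insufficiency, and nervous system abnormalities".
  - c) The third exception has no limit of grade or duration and reads "other toxicity that is higher than baseline level and related to cell therapy, classified as clinically meaningful severe and/or unacceptable toxicity", as judged by investigator and sponsor.

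Two further criteria stand beside (1) and do not require two patients:

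- Criterion (2): "Acute IPF exacerbation and severe adverse events that are related (possibly, probably or definitely related) to REGEND001 cell therapy".
- Criterion (3), which leaves the decision to judgement: "Adverse events that making investigator and sponsor believe the dose should not be escalated anymore, regardless of the event grade or reason".

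**The concern.** There are two separate errors.

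**Item c) is on the wrong side of the rule.** Related toxicity that investigator and sponsor call severe or unacceptable is listed as an exception to what counts. No stopping rule can intend that. The matching catch-all in the haematological part is counted, so c) was presumably meant to be counted too.

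**Item b) uses clinical events as examples of laboratory findings.** This gives them the longer exemption (7 days instead of 72 hours) and extends it to grade 4, which a) never exempts.

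Safety and tolerability are the primary purpose of the trial, and section 1.6 controls the move to higher doses. Section 9 uses the same criteria as a ground for halting the trial. Section 15.1.3.1 names cardiac arrhythmia as a risk of bronchoscopy, the delivery route, so the misfiled class is a relevant one.

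**Working it through.** No assumed event rate is needed. The check is textual, followed by applying the rule with the protocol's own limits.

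**Step 1. Does the protocol treat these events as laboratory findings?**

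- Sections 1.4, 1.5 and 10 list the electrocardiogram separately from laboratory examinations.
- Section 6.3 records rhythm under the ECG. Section 6.2, the laboratory list, has no test of rhythm, cardiac function or the nervous system.
- Section 12.3 puts electrocardiograms among other abnormal situations, apart from laboratory tests.
- Note 3 to the flowchart in section 1.4 assesses the nervous system in the physical examination.

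By this classification the three examples are non-laboratory events and belong under a).

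**Step 2. What counts under each item?** Inputs: a) exempts treated grade 3 up to 72 h; b) exempts treated grade 3 or 4 up to 7 × 24 = 168 h. For a treated, related cardiac or nervous system event, leaving c) aside:

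| Duration | Grade 3, b) as written | Grade 3, under a) | Grade 4, b) as written | Grade 4, under a) |
|---|---|---|---|---|
| 48 h | not counted | not counted | not counted | counted |
| 72 h | not counted | not counted | not counted | counted |
| 73 h | not counted | counted | not counted | counted |
| 120 h | not counted | counted | not counted | counted |
| 168 h | not counted | counted | not counted | counted |
| 169 h | counted | counted | counted | counted |

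At grade 3 the two readings differ over 168 − 72 = 96 h. Untreated events, events longer than 7 days and grade 5 events count under either item.

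**Step 3. Which of these differences change a stopping decision?**

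- *Grade 4:* none. Section 11.3 defines grade 4 as life-threatening, and section 12.1 makes a life-threatening event an SAE. If related, it ends escalation under criterion (2) from one patient, whichever of a) or b) applies.
- *Grade 3 and serious* (for example, hospitalised): none, for the same reason.
- *Grade 3 and not serious, over 72 h to 168 h:* here the outcome differs. Take the same related, treated, non-hospitalised grade 3 arrhythmia lasting 5 days (120 h) in two patients of one dose group. Since 72 < 120 ≤ 168, 0 of 2 count under b) and criterion (1) is not met. Under a), 2 of 2 count and escalation ends by rule.

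**Step 4. Item c).** It has no time limit and does not create the 96-hour band; it is a separate fault. Read literally, it removes from the count any other related toxicity that the two parties judge severe or unacceptable. Criterion (3) rests on the judgement of the same parties and would usually still stop escalation.

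**The case against.** The strongest reply is that little follows in practice.

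- **Item c).** Investigator and sponsor who call a toxicity unacceptable can already stop under criterion (3), from one patient and at any grade. This is a fair limit on the consequence. It does not make the text right, and it replaces a fixed rule with discretion.
- **Item b).** Several conditions must coincide: related, treated, grade 3, cardiac or neurological, over 72 hours to 7 days, non-serious, and the same or similar in two patients of one dose group. Section 11.3 describes grade 3 partly by hospitalisation and disability, which overlaps the SAE definition. Section 12.2 also has events of doubtful seriousness handled as SAEs until clarified. Both narrow the gap. Neither closes it, because section 12.1 does not count routine emergency department admissions as SAE hospitalisations, so a grade 3 arrhythmia managed there need not be serious.
- **Classification.** Sections 6 and 17.3.2 group the ECG with blood and urine tests as routine safety checks, and flowchart note 10 lists myocardial enzymes. But a routine safety check is not the same as a laboratory test, and enzymes do not measure rhythm, cardiac function or neurological status.
- **The word severe in criterion (2).** If it refers to severity grade, one related grade 3 event already stops escalation and the error in b) changes nothing. That reading is unlikely. Section 1.4 uses the term for a category beside adverse events, in the text and as a flowchart row. It would also leave the two-patient rule and the duration exceptions for grade 3 events without purpose.

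**Conclusion.** Both statements are wrong as written, and nothing elsewhere in the protocol corrects them. Item c) reverses its evident purpose, with a small practical effect because of criterion (3). Item b) leaves a narrow gap: for treated, related, non-serious grade 3 cardiac or nervous system events, a 96-hour band (over 72 h to 168 h) goes uncounted in criterion (1). Two such events in a dose group leave stopping to judgement where the rule should decide.

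This rests on reading severe adverse events in criterion (2) as serious adverse events. On the severity reading, b) has no effect on stopping, while c) remains misstated. No change in the probability of escalation is claimed, since that would need event rates the protocol does not give.

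The reach may be slightly wider. Section 1.3 adds three patients when one patient has an event that would terminate the study. If that phrase refers to the toxicities in section 1.6, the misfiling could also suppress this single-patient expansion. The correction should be made because it concerns a stated safety rule.

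**What to change.** Amend section 1.6, criterion (1), part 2):

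1. Take c) out of the exceptions and make it a counted item, parallel to the last haematological item.
2. Limit b) to true laboratory values and delete the cardiac and nervous system examples, so that such events fall under a).
3. Optionally, add a sentence saying that the exceptions apply only to criterion (1) and do not limit (2) or (3).

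The 72-hour and 7-day limits remain for the sponsor and investigators to set. The cost is a one-paragraph protocol correction with no new data.

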1.7 SAMPLE SIZE

This clinical research intends to enroll 15-24 idiopathic pulmonary fibrosis patients.

*If the patient drops out within 4 weeks after cell administration, additional patients should be supplemented in the corresponding dose group; if the drop out happens after 4 weeks, supplementary is not needed.

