1.3 DOSE-ESCALATION GROUPS

The standard dose of REGEND001 autologous therapy product is 1×10^6 cells /kg bodyweight /person.

Each dose group will enroll around 3-6 patients. Before starting the next dose group, safety evaluation must be done for 3 patients of the current dose group at 4 weeks post-transplantation. If 1 patient from a certain dose group undergo adverse events that would terminate the study within the evaluation window (28 days after receiving REGEND001 autologous therapy product), 3 more patients should be enrolled for this dose group; the next dose group cannot start unless none of the new enrolled 3 patients undergo adverse events that would terminate the study.

The first group with 3-6 patients, receiving a single administration at 0.6 times standard dose;

The second group with 3-6 patients, receiving a single administration at 1 times standard dose (the median safe dose in the previous clinical trial);

The third group with 3-6 patients, receiving a single administration at 2 times standard dose;

The fourth group with 6 patients, receiving a single administration at 3.3 times standard dose;

The following doses will be arranged according to the safety measures of these 4 dose groups.

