2.4 WITHDRAW CRITERIA

2.4.1 WITHDRAW DECIDED BY INVESTIGATOR

- (1) Patients with bad adherence, impacting the safety and tolerance evaluation;
- (2) Patients undergo adverse events, making the investigator believe further study is not suitable;
- (3) Other situations of the patient making the investigator believe further study is not suitable.

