2.4.2 WITHDRAW DECIDED BY PATIENT

- (1) Patients have the right to withdraw for any reason;
- (2) Even though the patient has not officially withdrawn, follow-up, cell administration, or examinations were not conducted successfully as required by the protocol.

If the patient withdraws before finishing the study, the withdraw reason should be recorded in CRF and original note.

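### Withdrawal after the single dose can end safety observation for outcome-related reasons, and Section 1.7 replaces every dropout before week 4 without saying whether the replaced patient still counts for escalation

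*Protocol*

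**What the plan says.** - **Treatment.** Protocol 1.3 and 3.3 plan one administration. Section 1.4 gives no further REGEND001 during follow-up, which runs to V9 at week 24. The primary outcome (8.1) is the incidence and severity of related adverse events over those 24 weeks.
- **Withdrawal.** Under 2.4.1(2) the investigator may withdraw a patient in this case: "Patients undergo adverse events, making the investigator believe further study is not suitable". Under 2.4.2(2) a patient who has not formally left is listed as withdrawn when "follow-up, cell administration, or examinations were not conducted successfully as required by the protocol". Neither rule separates patients already dosed from those not yet dosed.
- **Follow-up after withdrawal.** The flowchart in 1.4 has an early-withdrawal visit at which AEs and SAEs are collected. Note 18 continues follow-up beyond that visit only if a clinically significant abnormality was reported at withdrawal.
- **Replacement.** Section 1.7 states: "If the patient drops out within 4 weeks after cell administration, additional patients should be supplemented in the corresponding dose group". After 4 weeks there is no replacement. The reason for leaving plays no part.
- **Escalation.** Section 1.3 requires that "safety evaluation must be done for 3 patients of the current dose group at 4 weeks post-transplantation". One terminating event within 28 days brings in three more patients, and "the next dose group cannot start unless none of the new enrolled 3 patients undergo adverse events that would terminate the study".

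**The concern.** Once the dose is in the lung, a withdrawal rule cannot reduce exposure. It can only decide who continues to be observed. Here two of the grounds are tied to outcome: an adverse event, and a visit or examination that did not succeed. In IPF, deterioration is one plausible reason for an unsuccessful examination. Observation can therefore end early in the patients whose safety course matters most.

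Two things are at stake.

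1. **The 24-week endpoint.** A patient who leaves at week 2 with no clinically significant abnormality reported has no required AE collection from then to week 24. A related event that first appears in that period may never be recorded. It would also be unavailable to 1.6, which considers events over the whole study period and names related acute IPF exacerbation and related severe adverse events as grounds for ending escalation.
2. **The week-4 escalation check.** The 4-week replacement limit coincides with the 28-day evaluation window. A replacement can supply the third week-4 evaluation, and nothing says whether the patient replaced remains in the group on which the decision is made. With three patients per group, the status of one patient can decide it.

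**Working it through.** **Step 1: the plan's own sample size.** Section 1.7 states: "This clinical research intends to enroll 15-24 idiopathic pulmonary fibrosis patients". In 1.3 the group sizes run from "The first group with 3-6 patients, receiving a single administration at 0.6 times standard dose", with the same range for groups 2 and 3, to "The fourth group with 6 patients, receiving a single administration at 3.3 times standard dose".

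- Minimum: 3 + 3 + 3 + 6 = 15
- Maximum: 6 + 6 + 6 + 6 = 24

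Both ends reproduce exactly. The range is the sum of the group sizes, with no allowance for patients dosed and then replaced. This does not show that a replacement takes over the first patient's place in the count, but it leaves that possible.

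**Step 2: what happens to a dosed patient who leaves before week 4.**

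| Question | Where | Answer in the protocol |
|---|---|---|
| Are events before withdrawal recorded? | 11.2; flowchart in 1.4 | Yes |
| Do they enter the safety data? | 17.2, Safety Set | Yes, although the set may exclude some cases, with one example as the only limit |
| Do they count toward the triggers? | 1.3, 1.6 | Events in patients of the dose group; completion is not required |
| Is the patient still one of those evaluated at week 4? | 1.3, 1.7 | Not stated |
| Are events first arising after withdrawal collected to week 24? | Note 18 | Not required unless an abnormality was reported at withdrawal |

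The gap lies in the last two rows.

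**Step 3: illustration of the escalation check.** The protocol gives no event rate and no share of patients withdrawn, so both inputs are assumptions:

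- p: true probability of a terminating event within 28 days
- q: share of patients with such an event who leave, are replaced and are not counted

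Under 1.3 a dose clears with 0 of 3 events, or with 1 of 3 followed by 0 of 3. Two or more of the first three are taken as not clearing. The separate grounds in 1.6(2) and 1.6(3) are left out.

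P(clear) = (1 − r)³ + 3r(1 − r)²(1 − r)³ = (1 − r)³ + 3r(1 − r)⁵

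where r is the event rate among patients counted: r = p(1 − q)/(1 − pq).

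For p = 0.30:

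- q = 0: r = 0.30; 0.343 + 0.151 = 0.494
- q = 0.25: r = 0.225/0.925 = 0.243; P = 0.614
- q = 0.50: r = 0.15/0.85 = 0.176; P = 0.759

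For p = 0.50:

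- q = 0: 0.125 + 0.047 = 0.172
- q = 0.25: r = 0.375/0.875 = 0.429; P = 0.265
- q = 0.50: r = 0.25/0.75 = 0.333; P = 0.428

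If events are counted before the patient is replaced, q = 0 and nothing changes: 0.494 and 0.172. The calculation shows the direction and possible range under one reading. It does not estimate what the protocol will do.

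**The case against.** A reader might infer that patients with problems disappear from the 28-day evaluation and from the primary endpoint. The protocol does not support that.

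- The trigger in 1.3 is an event in a patient of the dose group, and 1.6 counts events reported in patients of the same group. Neither requires the patient to reach week 4. Section 1.7 adds patients and does not say that the first patient's event is dropped. Section 1.6(3) also allows any event, of any grade or cause, to halt escalation.
- AEs are recorded from cell collection onward (11.2), the early-withdrawal visit collects AEs and SAEs, AEs are followed until their outcome is clear (1.4), and SAEs are followed to resolution, stabilisation, death or loss (12.2).
- A patient withdrawn because of a related AE is already a case in the numerator, so later unobserved events cannot lower the proportion of patients with a related AE on that patient's account.
- Section 2.4.2(2) stands under withdrawal by the patient and can be read as meaning non-attendance. Death is not among the grounds in 2.4, and whether it counts as dropping out under 1.7 is not stated.

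All of this stands, and it rules out the stronger reading. It does not restore the missing week-4 assessment, does not require collection of events that first arise after withdrawal, and does not say whether a replaced patient remains among those evaluated. Nor is this matter that can be left to an SAP: withdrawal, replacement and follow-up govern conduct at the sites and are fixed in this document.

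**Conclusion.** The point holds in two limited parts. First, related AEs that first arise after an outcome-related withdrawal can be missed from the 24-week primary endpoint, because nothing requires a withdrawn dosed patient to be followed to V9. Second, the three patients evaluated at week 4 can be selected completers, because replacement ignores the reason for leaving and 1.3 is silent on the patient replaced.

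Neither part can be sized from the protocol. The rise from 49% to 61% or 76% at a true event rate of 30% (17% to 27% or 43% at 50%) rests on two assumptions: the event rate itself, and that 25% or 50% of patients with events are replaced and not counted. No section states such a practice, and the triggers in 1.3 and 1.6 point the other way. If events are counted first, the change is zero. The point is still worth settling before enrolment, because the trial's primary purpose is safety and tolerability and its escalation decisions rest on very small groups.

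**What to change.** - **Section 2.4.** State that a dosed patient withdrawn under 2.4 continues safety follow-up to V9 unless consent is withdrawn. Keep the investigator's power to withdraw, but separate it from the end of safety observation. Reconcile the wording with section 14, which requires a pregnant subject to withdraw from the trial.
- **Section 2.4.2(2).** State that after V4 a missed or failed visit or examination is a missing value, not a withdrawal. Align note 18 with this.
- **Section 1.7, with a cross-reference in 1.3.** For the escalation decision, replace only patients who become unevaluable within 28 days for reasons unrelated to safety. A patient who dies or leaves because of an AE stays in the evaluated group and is assessed against the existing criteria in 1.3 and 1.6.
- **Section 17.2.** State that all dosed patients, including those replaced, stay in the safety denominator.

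The cost is a few sentences and a few more follow-up contacts. The range of 15 to 24 can stand as the number of evaluable patients, with replacements added to it. For illustration, an assumed early dropout of 10% would mean 15/0.9 = 16.7 to 24/0.9 = 26.7, that is 17 to 27 patients dosed.
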